Following randomization, participants will briefly speak with the study therapist to receive an introduction to their assigned study condition (either PPMI or EUC) and will receive the specific condition materials (i.e. a Participant Workbook for those in the PPMI condition, a study developed resource guide, a study timeline and payment FAQ sheet, and two brochures on pain management and buprenorphine for those in the EUC condition). This first encounter with the study therapist in each condition will be conducted in person, whenever possible, at the clinic where their buprenorphine provider is based or at a location in the community in order to provide the participant with session materials and to build rapport between the therapist and participant in order to increase the likelihood the participant will engage in the remotely delivered sessions. If in-person is not possible, study therapist will speak with the participant by phone and discuss the option of video chatting for future session. Each of the 8 PPMI sessions are estimated to last approximately 60 minutes each, whereas the 2 EUC sessions will likely last between 5-10 minutes each. Following the initial interaction for both conditions, the sessions will be delivered via phone or video chat to maximize engagement and reach for potential future implementation in rural areas with limited access to treatment. Participants will be provided information regarding how to contact the study therapist for their sessions and instructed to complete the sessions in a quiet location where they are relatively free from distractions in order to allow for maximum engagement with the study materials. Study therapists may end sessions early or reschedule sessions at their discretion if they feel continuing is not in the best interest of the participant (e.g. if a participant reports they are driving or currently using substances during the session). Any missed or incomplete sessions will be rescheduled for a later date. Participants will provide feedback on the quality and relevance of the session material (both PPMI and EUC) via a post-treatment self-report survey at follow-up.

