Although the PPMI is the active intervention condition being tested during the trial, the EUC condition is designed to match the PPMI condition in terms of the non-specific aspects of receiving support and information regarding buprenorphine and pain management, therefore this project was designed to be a direct comparison between PPMI and an EUC condition. This design was chosen because limited data exist on the longer-term efficacy of the PPMI approach in individuals with OUDs and chronic pain receiving buprenorphine treatment, and no other short-term approach has evidence in terms of buprenorphine related outcomes supporting its efficacy in this population. The first and most important step in this line of research is to establish that the intervention is efficacious. This study design, then, provides a clear comparison group to determine whether or not

main effects may be due to the intervention components and not merely contact with a therapist.

Intervention receipt

Determining the level of intervention receipt among participants will be established through various methods. Straight session attendance will be calculated by summing the number of sessions the participant completed. From here, participants may be categorized into those who received no study condition (e.g. completed zero sessions in either the PPMI or EUC condition), those who received a partial dose of the study condition (e.g. completed fewer than 4 sessions for the PPMI condition and only 1 session for the EUC condition, or those who received the full dose of the study condition (e.g. completed all 8 sessions for the PPMI condition and 2 sessions for the EUC condition).

Content of PPMI and EUC conditions

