The **EUC condition** is designed to match the PPMI condition in terms of the non-specific aspects of receiving support for pain, substance use, and receiving monitoring of buprenorphine adherence. We have used modified versions of attention control conditions in two studies of pain (one funded by VA HSR&D and one funded by NIDA) as well as our work on suicide prevention in those with substance use disorders (one prior NIDA R21 and one ongoing study funded by the Department of Defense). The EUC condition for this study will involve 2 brief sessions (5-10 minutes in length) delivered via phone or video chat in which the study therapist will discuss a study-developed resource guide and two brochures (one on chronic pain and one on buprenorphine treatment) with the participant. When using video chat, the research therapist will have the ability to display the condition materials on the screen. The participant will be asked if they have any questions related to the material presented in the brochures and will provide education and support to the participant during the brief session. Thus, the EUC condition will provide a comparable level of contact with a study therapist who will provide support on topics that are relevant to the participant, however the materials will not overlap with the content of the PPMI condition. Patients randomly assigned to the EUC condition will receive the condition materials (e.g. brochures with the resource guide) during the initial in-person meeting with the study therapist, when possible. If unable to meet in person, the study materials will be emailed and mailed to the participant. While not directly intended to be therapeutic in nature, these brief sessions may help patients to better understand the origins and consequences of pain and substance use in their life. Topics related to psychological factors associated with pain and possible psychosocial coping mechanisms will not be a part of the formal content of the sessions.

Treatment as Usual

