PPMI condition (8 sessions)	1 hour each (8 hours total)	\$40 for phone use	Phone
EUC condition (2 sessions)	5-10 minutes each (10-20 minutes total)	\$40 for phone use	Phone
Weekly Surveys (13 total)	5 minutes each (65 minutes total)	\$10 each (+ \$10 for completing all)	Phone / Online
1-month follow up	1.5 hours	\$40 (+ \$10 for urine sample)	In-person / Phone / Online
3-month follow up	1.5 hours	\$40 (+ \$10 for urine sample)	In-person / Phone / Online
6-month follow up	1.5 hours	\$40 (+ \$10 for urine sample)	In-person / Phone / Online
9-month follow up	1.5 hours	\$40 (+ \$10 for urine sample)	In-person / Phone / Online
12-month follow up	1.5 hours	\$50 (+ \$10 for urine sample)	In-person / Phone / Online
	Total	\$500	

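### The control arm is said to give comparable therapist contact, but planned session time is 480 minutes against 10–20, so effects cannot be credited to content rather than contact

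*Combined protocol and SAP*

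**What the plan says.** Section 5.1 makes three linked statements about the control arm.

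- On matching: "the EUC condition is designed to match the PPMI condition in terms of the non-specific aspects of receiving support and information". This is given as the reason for comparing the two conditions directly.
- On inference: the design is said to provide a comparison group that can determine whether "main effects may be due to the intervention components and not merely contact with a therapist".
- On contact, in the description of EUC content: "the EUC condition will provide a comparable level of contact with a study therapist".

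The same section gives the schedule: "Each of the 8 PPMI sessions are estimated to last approximately 60 minutes each, whereas the 2 EUC sessions will likely last between 5-10 minutes". The paragraph that calls contact comparable also says: "The EUC condition for this study will involve 2 brief sessions (5-10 minutes in length) delivered via phone or video chat". The activity table in section 6.2 gives the totals, "1 hour each (8 hours total" for PPMI and "5-10 minutes each (10-20 minutes total" for EUC.

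Other places are more cautious. The Précis claims only that EUC offers some contact and education. Section 6.2.3 (Blinding) acknowledges the 8 versus 2 sessions and describes a test of PPMI's benefit over and above usual community care.

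**The concern.** A control arm can separate what is said in therapy from time spent with a therapist only if therapist time is similar in both arms. Here the amount of contact differs as sharply as the content does, so the two are confounded by arm. An advantage for PPMI would be compatible with an effect of the CBT and acceptance content, with an effect of about eight hours of individual attention, or with both.

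What is at stake is the conclusion, not the test. Section 2.1 says the mixed-methods work will help explain PPMI's mechanisms of action, and section 1.2 aims to identify its key elements. If the reading in section 5.1 is carried into the report, specific components could be credited with an effect that the design cannot attribute to them. For a trial meant to inform implementation, that bears on what others would choose to deliver.

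**Working it through.** **Inputs**

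- PPMI: 8 sessions of about 60 minutes (section 5.1).
- EUC: 2 sessions of 5–10 minutes (section 5.1).
- Stated totals: 8 hours and 10–20 minutes (activity table, section 6.2).
- Per-protocol minimum: 4 PPMI sessions or 1 EUC session (sections 5.4 and 9.3).
- Introductory contact with the therapist: given in both arms, described as brief, length not stated (section 5.1).

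**Reproducing the stated totals** (sessions × minutes per session)

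- PPMI: 8 × 60 = 480 minutes = 8 hours.
- EUC: 2 × 5 = 10 minutes to 2 × 10 = 20 minutes.

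Both agree with the table.

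**Comparing the arms on planned session time**

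- Ratio: 480/20 = 24 to 480/10 = 48.
- Difference: 480 − 20 = 460 to 480 − 10 = 470 minutes.
- Number of sessions: 8/2 = 4 times as many.

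**Does a different basis of comparison rescue the claim?**

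- At the per-protocol minimum: 4 × 60 = 240 minutes against 5–10 minutes, so 240/10 = 24 to 240/5 = 48.
- A PPMI participant who attends one session only: 60/20 = 3 to 60/10 = 6 times the whole EUC programme.
- Adding an introductory contact of T minutes to both arms gives a ratio from (480 + T)/(20 + T) to (480 + T)/(10 + T). T is an assumption, because the protocol gives no figure:

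| T (minutes) | Lower ratio | Upper ratio |
|---|---|---|
| 0 | 24.0 | 48.0 |
| 10 | 490/30 = 16.3 | 490/20 = 24.5 |
| 30 | 510/50 = 10.2 | 510/40 = 12.75 |
| 60 | 540/80 = 6.75 | 540/70 = 7.7 |

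Even an hour of introduction, hardly brief, leaves PPMI with about seven times the contact. The absolute gap of 460–470 minutes does not change with T.

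**Can the planned analyses separate content from contact?**

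- Section 9.6 proposes to explore adjustment for, and mediation by, session attendance. Attendance is observed after randomisation, and each PPMI session delivers content and contact together, so it cannot distinguish them.
- Section 1.3 proposes mediators such as pain self-efficacy, catastrophizing and acceptance. These could also respond to therapist attention, so a mediated effect would not show that content was responsible.

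**The case against.** The best case for the plan has four parts.

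1. **Nothing confirmatory depends on the wording.** The primary hypothesis, the intention-to-treat Cox model and the sample size concern PPMI against EUC, and none assumes equal contact. This stands in full, and it limits the point to interpretation.
2. **The imbalance is disclosed, and better wording already exists.** The session lengths are stated openly, and the Précis and section 6.2.3 describe the comparison accurately. The disclosure is real, but it does not make the inference in section 5.1 available. The accurate passages contradict section 5.1 rather than correct it.
3. **The matching claim is about non-specific support, not minutes.** Both arms use manuals, the same masters-level therapists, the same remote delivery and the same 4–6 week window, and therapists are told to give similar attention within a session. Those features are matched. However, section 5.1 also speaks of the level of contact, and similar attention within a session does not equalise the number or length of sessions.
4. **The size and consequence can be overstated.** The 24- to 48-fold figure counts planned session minutes only and falls once the introductory contact is included. Attribution to components would be unsupported, not shown to be false. Both qualifications are correct, and neither makes contact comparable.

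**Conclusion.** The statement is wrong as written. On the protocol's own figures, planned session contact is 480 minutes in PPMI and 10–20 minutes in EUC: 24 to 48 times more, a gap of 460–470 minutes. The ratio rests on planned session times, not attended ones, and excludes the introductory contact; allowing up to 60 minutes for that in each arm still leaves a ratio of about 7 to 8.

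The design therefore lacks a property that section 5.1 claims for it. The trial can estimate the effect of being assigned to the PPMI package rather than to brief education. It cannot say whether any effect comes from the intervention's components or from contact with a therapist. The choice of EUC, the randomised comparison, the primary analysis and the sample size are unaffected.

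**What to change.** Amend section 5.1 as follows.

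- In the description of EUC content, replace the comparable-contact statement with the weaker description already used in the Précis, and give the planned totals (about 8 hours against 10–20 minutes).
- Delete the sentence that the design can distinguish component effects from mere contact.
- Limit both matching statements to what is matched: use of a manual, therapists, remote delivery and delivery window.
- Add one sentence stating that the trial estimates PPMI as a package, content plus about eight hours of therapist contact, against brief education, and that effects cannot be attributed to particular components. Apply the same limit when reporting the attendance and mediation analyses.

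The cost is wording and a narrower stated conclusion. Procedures, sample size and analyses stay as they are. A control matched on therapist time would address the component question, but that would be a different trial and is not needed for the one planned.

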Both the PPMI and EUC conditions will be overlaid onto an episode of OUD treatment with buprenorphine at an outpatient clinic. While we will be recruiting from multiple predetermined recruitment sites (listed above in Section 4. "Selection and Enrollment of Participants"), we will also be recruiting from the community through posted flyers, newsletters, social media/online platforms, and the project website. We may not be aware of the specific treatment requirements or programming at all locations that potential participants may be receiving their buprenorphine treatment. Due to the varied nature of buprenorphine treatment at outpatient substance use clinics, it is unlikely that participants across sites will receive the same treatment experience. However, since all participants will currently be receiving buprenorphine for the treatment of an OUD through a provider's prescription, we assume that participants will all be receiving the minimal standard of care dictated in the buprenorphine prescription guidelines (e.g. regularly meeting with their prescribing physician in order to renew their prescription). The level of participant involvement with their buprenorphine provider (e.g. frequency of appointments, requirements for outside counseling in addition to buprenorphine treatment, requirements for providing drug screens, etc.) may vary from clinic to clinic, as will exposure to other forms of substance use treatment (e.g. relapse prevention) and/or 12-step principles to encourage abstinence and improve coping skills. We will

ask participants to provide information regarding treatment experiences during the baseline (enrollment) interview and at all follow-up assessments in order to control for any potential confounding factors during analyses. No efforts will be made to influence the prescribing practices of other providers and study therapists will be barred from discussing clinical information about participants with any treatment providers, except in cases in which reporting (ex. suicide, homicide, child abuse) is clinically necessary.

Information/data sharing with the participant's provider

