5.3.1 Allowed Interventions

Participants may continue to take any prescribed medications including medications for physical health conditions, mental health conditions, or medications for the treatment of OUDs, including buprenorphine during their study participation. Participants may continue to take prescription opioid medications and/or other prescription medications for the treatment of a substance use disorder (e.g. disulfiram). Participants may be required by their treatment provider to participate in some form of outpatient counseling (including CBT treatment) or recovery self-help groups as a requirement of remaining on buprenorphine through the treatment clinic. Because remaining in buprenorphine treatment is the primary outcome in this study, involvement in these auxiliary treatments will be allowed. Data will be collected during all study assessments to capture the scope and frequency of the participant's involvement in additional treatment activities during their time on study. Participants may also be receiving medical care or treatment for a pain condition (e.g. physical therapy, acupuncture, etc.) while in the study. When possible, treatment records at the study sites will be reviewed to gather information regarding participant treatment involvement during the study. Where treatment records are not available or accessible through a signed release of information, participant self-report of treatment involvement collected at follow-up will be used to track treatment involvement.

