- **Treatment Service utilization.** In order to obtain data about treatment utilization, past six-month history of treatment (for drugs and/or alcohol and mental health) will be obtained at the baseline interview with items adapted from the National Epidemiologic Survey on Alcohol and Related Conditions (NESARC) and used in prior work. This instrument elicits information about formal specialty substance use and mental health treatment services (both inpatient and outpatient), primary care brief interventions, and

self-help groups. These questions will be modified and repeated at subsequent follow-up to cover the interval of time since last interview.

- **Medical record abstraction (Where applicable and allowable by the individual sites)**
Participant electronic medical records may be accessed by research study staff to collect information regarding buprenorphine treatment involvement. HIPAA authorization may be included in Part 2 (site information) of the informed consent or participants may be asked to sign a release of information if applicable.

Participants will also be asked to provide a voluntary urine sample for the baseline assessment and all follow-up assessments (i.e. 1-, 3-, 6-, 9-, and 12-months post enrollment) to analyze for recent substance and medication use. For each sample provided, the participant will receive an additional \$10 payment (total possible study compensation for urine samples is \$60). Our study team has experience collecting urine drug screens from several previous studies, and we have learned techniques for maintaining participant confidentiality during this process (e.g., providing participants with a bag for transporting the screening cup, checking the screen in a private location). When unable to complete an assessment in-person, participants will have the option to complete a urine drug test at home. Research staff will mail the urine sample cup with instructions on how to complete the test and submit a photo of the results to the research team via a link for upload or report results over the phone. We will be using the CLIA Waived UScreen Drugs of Abuse Cup with Adulterants to collect the urine specimen for testing. The test cups can detect up to 12 illicit and prescription drugs in one testing with up to a 99% accuracy rate. The model used in this study also has a built-in temperature strip.

This model will test for the following substances:

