9.6 Data Analyses

This study will utilize an intent-to-treat approach where the primary analyses will examine the association between randomization to condition and the treatment outcomes, irrespective of how much of the intervention or control conditions the participants attended. However, in exploratory analyses, the study will explore how controlling for session attendance influences the primary results and whether session attendance mediates the potential effects of assignment to treatment condition on the subsequent outcomes. The PI, data manager, and project biostatisticians and/or data analysts will analyze the data using SAS software. The primary specific aims will focus on pain (level, tolerance and pain-related disability) and substance use (frequency of drug, alcohol and opioid use) outcomes. Outcome data will be analyzed using mixed model regression analyses. The alpha level will be set at 5%.

As stated previously, the primary aims are:

Primary Aim 1: Conduct a randomized controlled trial (RCT) comparing a remotely delivered PPMI (n=100) to EUC (n=100) to assess the impact of randomization to PPMI on retention on buprenorphine treatment over 3-months.

Research Hypotheses for Primary Aim 1: Participants in the PPMI condition will have greater retention on buprenorphine treatment (i.e., lower treatment dropout): up to 3-months. The primary goals for the project are to test the preliminary efficacy of an 8-session Psychosocial Pain Management Intervention (PPMI), as compared to an EUC control condition, on retention on buprenorphine treatment. We will evaluate measures of self-reported information gained from the TLFB on buprenorphine treatment use on a daily basis and data collected from weekly surveys completed by the participant. For those with multiple sources of information available (TLFB and self-report survey), we will use the comparison between sources of data to develop reasonable assumptions about actual consumption. It is anticipated that individuals will occasionally miss a day of buprenorphine treatment without having dropped out of treatment. Discontinuation of treatment will be operationalized as 7 days in a row without taking buprenorphine. Analysis will follow a time-to-event (survival analysis) framework where the outcome is time until discontinuing buprenorphine treatment.

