We will first descriptively calculate the percent still receiving buprenorphine at the 1- and 3-month follow-ups. The independent variable of interest is an indicator of group (PPMI vs.

EUC). Analysis will use an intent-to-treat framework, where participants are classified by the condition they were randomized to, regardless of what they received. Cox Proportional Hazards regression models will be used to test the association between group assignment and time to dropping out of buprenorphine treatment at 3-months. We will test if assumptions for this modeling technique are met, and if they are not, consider including a covariate*time interaction or stratification in Cox modeling, or variable transformations or alternative modeling strategies, if necessary.

The secondary aims are:

Secondary Aim 1: Conduct a randomized controlled trial (RCT) comparing remotely delivered PPMI (n=100) to EUC (n=100) to assess the impact of randomization to PPMI on retention on buprenorphine treatment over 12-months.

Secondary Aim 2: Determine the impact of remotely delivered PPMI on pain level, pain-related functioning, and frequency of substance use over 3-months.

Secondary Aim 3: Determine the impact of remotely delivered PPMI on pain level, pain-related functioning, and frequency of substance use over 12-months.

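### Section 5.1 collects follow-up treatment data to control for confounding, without limiting adjustment to baseline; section 9.6 does not use it but does not rule it out

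*Combined protocol and SAP*

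**What the plan says.** Section 5.1 (Treatment as Usual) explains that background care will differ between clinics. Its examples include "The level of participant involvement with their buprenorphine provider (e.g. frequency of appointments, requirements for outside counseling in addition to buprenorphine treatment", as well as drug-screen rules and exposure to other addiction treatment or 12-step programmes. It then says information on treatment experiences is collected at enrolment and "at all follow-up assessments in order to control for any potential confounding factors during analyses". No variable, model or time point for the adjustment is named, and it is not labelled exploratory.

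Section 5.3.1 says a provider may require "outpatient counseling (including CBT treatment) or recovery self-help groups as a requirement of remaining on buprenorphine through the treatment clinic". Section 6.2.2 describes a six-month treatment history at baseline and adds: "These questions will be modified and repeated at subsequent follow-up to cover the interval of time since last interview". The schedule in section 6.1 lists the Treatment Services Review at baseline and at every follow-up.

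In section 9.6, the retention analysis is specified as follows: "Analysis will follow a time-to-event (survival analysis) framework where the outcome is time until discontinuing buprenorphine treatment". For the Cox model, "The independent variable of interest is an indicator of group", and no adjustment covariate is named. An unnamed covariate appears only among the remedies if model assumptions fail. The mixed model for pain and functioning lists the baseline value, time and group. The one post-randomisation adjustment that section 9.6 names is session attendance, and that is exploratory.

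**The concern.** A confounder of the arm comparison would have to influence which arm a participant is in. Arm is assigned at random, so care received later cannot do that, and pre-existing differences in care are balanced in expectation. Baseline treatment history can be a legitimate covariate. Follow-up treatment use cannot serve the purpose that section 5.1 gives it.

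It may also be partly a result of the outcome. If a clinic ties counselling to staying on buprenorphine, use of that counselling depends on retention, and it is recorded over the same interval in which the primary event occurs. Appointment frequency is closer still: section 9.5.1 lists completed appointments with the buprenorphine provider among the record items reviewed in its account of how retention is collected. PPMI may also change outside care directly, because its content covers engagement at the clinic and barriers to treatment. Holding such a variable fixed compares arms among people with similar retention and so removes part of the effect under test.

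For pain and substance use the direction is not predictable. Outside care may also rise after relapse, since section 7 has staff refer participants after acute substance-related events and encourage those out of treatment to return.

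**Working it through.** **Inputs from section 9.2.** 100 per arm, EUC event rate 50%, hazard ratio 0.5, two-sided alpha 0.05, stated power above 85%, no loss allowed for the primary outcome.

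**The plan's own figure.**
- PPMI event probability: 1 − (1 − 0.5)^0.5 = 0.293.
- Expected events: 100 × 0.50 + 100 × 0.293 = 79.3.
- Schoenfeld: z = √79.3 × ln 2 / 2 − 1.96 = 3.086 − 1.96 = 1.126, power 87.0%.
- Freedman: z = √79.3 × (1 − 0.5)/(1 + 0.5) − 1.96 = 2.968 − 1.96 = 1.008, power 84.3%.

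The stated power reproduces to within about one point under the more conservative formula. Schoenfeld needs 75 events for 85% and Freedman 81, against 79.3 expected, so there is little margin.

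**Effect of adjusting.** The documents give no rates of outside treatment by buprenorphine status, so these are assumed and shown as a range. Drop-out times were simulated as exponential, with rate ln 2 / 91 per day in EUC and half that in PPMI, censored at 91 days, with 400 trials per row. Each trial was fitted by a Cox model with group only, then with group plus one follow-up treatment covariate. The first five rows use a yes/no covariate whose probability depends on whether the participant is still on buprenorphine. The last four use a count of contacts over 13 weeks, accruing at one weekly rate on buprenorphine and another after stopping.

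| Covariate, assumed on / off | HR, group only | HR, adjusted | Power, group only | Power, adjusted |
|---|---|---|---|---|
| Yes/no, 0.5 / 0.5 | 0.49 | 0.49 | 87.0% | 86.5% |
| Yes/no, 0.6 / 0.4 | 0.50 | 0.50 | 86.2% | 84.5% |
| Yes/no, 0.7 / 0.3 | 0.50 | 0.54 | 84.0% | 79.0% |
| Yes/no, 0.8 / 0.2 | 0.51 | 0.59 | 83.2% | 65.5% |
| Yes/no, 0.9 / 0.1 | 0.49 | 0.67 | 88.0% | 39.0% |
| Contacts per week, 0.5 / 0.5 | 0.50 | 0.50 | 86.8% | 87.0% |
| Contacts per week, 0.5 / 0.25 | 0.50 | 0.52 | 85.8% | 81.0% |
| Contacts per week, 1 / 0.25 | 0.51 | 0.60 | 83.2% | 54.8% |
| Contacts per week, 1 / 0 | 0.51 | 0.67 | 84.8% | 37.5% |

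Monte Carlo error is about 1.7 points at 87% power (√(0.87 × 0.13 / 400)) and 2.5 points at 50% (√(0.5 × 0.5 / 400)), so the variation in the group-only column is noise. The two rows without dependence show no attenuation, and the loss grows with the dependence in both forms of the covariate.

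**The case against.** The strongest reply is that the plan does not specify this adjustment. The Cox models name only group, and the mixed model for pain and functioning lists its terms without any for outside treatment. Section 9.1 promises that the main tests are fixed in advance and kept apart from exploratory work. On this view section 5.1 merely explains data collection. It includes baseline ("ask participants to provide information regarding treatment experiences during the baseline (enrollment) interview and at all follow-up assessments in order to control for" unspecified confounders), where adjustment is harmless, and section 5.3.1 gives a descriptive reason for collecting much the same information. This stands. A reader might infer that the primary estimate is biased by design, but the documents do not support that.

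The second reply concerns the causal link. Section 5.3.1 says only that counselling may be required. A reader might infer that anyone who stops buprenorphine loses counselling, but no section says so. The event is a run of 7 or more days without the drug, not discharge, so a participant can have the event and still be prescribed buprenorphine or attend counselling. Treatment use is asked over an interval, so counselling before the gap still counts. Pain care and voluntary self-help need not track retention at all. All of this stands and argues against assuming the strongest dependence; the contact-count rows allow for use before the gap and still show a loss.

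What the replies do not remove is the stated purpose itself. It covers follow-up data, is not marked exploratory as the session-attendance adjustment is, and is not excluded anywhere in section 9. An analyst who added such a term could cite the protocol for it.

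**Conclusion.** Section 5.1 is wrong as written in one respect: controlling for confounding is not a valid use of treatment data collected after randomisation. This conflicts with the models named in section 9.6 and leaves open an adjustment that could dilute the primary result; it does not show that the result will be diluted.

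If the adjustment were applied to the retention model, a true hazard ratio of 0.50 would become about 0.50 to 0.67, and power would fall from about 87% to between 85% and 38%, under weak to strong assumed dependence of outside treatment on staying on buprenorphine. With no dependence the loss is nil. These figures rest on exponential drop-out, a single covariate and assumed treatment rates; nothing in the documents says where in the range the trial would lie. For pain and substance use no size was computed and no direction is claimed.

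**What to change.** Reconcile section 5.1 with section 9.6 by one sentence in each:
- The confirmatory primary and secondary models use only group, the stratification factors (sex, past-year heroin use, veteran status) and pre-randomisation covariates, which may include the baseline treatment history already collected.
- Treatment use reported at follow-up is summarised by arm as co-treatment received, or enters only analyses labelled exploratory or mediation.

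Data collection, sample size and planned power are unchanged. The cost is the amendment text.
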